### 5.2.2 OTHER VARIABLES

We will use following criteria to adjudicate safety outcomes from intervention initiation to 12 hours following discontinuation of CRKT.

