#### 8.3.2 REFERENCE MEASUREMENTS

The following data will provide the basis for assessing protocol compliance and safety as well as between-group differences. Data for each of the variables will be recorded on the days shown in the Time-Events schedule ([Appendix F](#)) until death, discharge from the ICU, or day 28, whichever occurs first. Values will be derived from clinically available data.

1.  $UF_{NET}$  rate
  - a. Restrictive  $UF_{NET}$  rate group
    - i. Time and initial  $UF_{NET}$  rate
    - ii. Time and target  $UF_{NET}$  rate
    - iii. Time and hourly  $UF_{NET}$  rate

- iv. Reason and duration of UFNET hold (if any)
- v. Total volume of UFNET during the study
- vi. Rescue UFNET (YES/NO)
  
- b. Liberal UFNET rate group
  - i. Time and initial UFNET rate
  - ii. Time and target UFNET rate
  - iii. Time and hourly UFNET rate
  - iv. Reason and duration of UFNET hold (if any)
  - v. Total volume of UFNET during the study
  - vi. Rescue UFNET (YES/NO)

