## 13 SAFETY MONITORING

### 13.1 ADVERSE EVENTS

A clinical trial adverse event (AE) is defined as any untoward medical event temporally associated with the use of drug or study procedure in humans, whether or not it is considered related to a study intervention or study procedure. Assuring patient safety is an essential component of this protocol and the Principal Investigators have the primary responsibility for the safety of the individual participants. Thus, the Principal Investigators

will monitor for all AEs from study enrollment until ICU discharge or day 28, whichever occurs first.

Following study enrollment, AEs occurring after the patient received the study interventions will be evaluated at the two clinical sites by the Principal Investigators. Investigators will assess if there is a reasonable possibility that the study procedure caused the event, based on the criteria outlined in [Appendix G1](#).

If a patient's study treatment is discontinued because of an AE, the study investigator must report the circumstances and data leading to discontinuation of treatment in the AE case report forms. AEs will be considered related or possibly related to study treatment only up to 24 hours following discontinuation of CKRT. AEs occurring after discontinuation of CKRT and after transition to IHD will not be considered related to study interventions.

Investigators will also consider if the event is unanticipated or unexplained given the patient's clinical course, previous medical conditions, and concomitant medications as outlined in [Appendix G2](#). An adverse event is considered "unanticipated" if it is not listed in the study protocol (21 CFR 312.32(a)).

The following adverse events will be collected in the case report forms:

- Serious adverse events
- Non-serious adverse events that are considered by the investigator to be related to study intervention or study procedures or of uncertain relationship ([Appendix G](#))
- New onset hypotensive and hypertensive episodes, cardiac arrhythmias, considered by the investigator to be related to rate of fluid removal during CKRT, or of uncertain relationship
- Emergent use of rescue UFNET rates with rates higher than the assigned treatment arm
- Severe hypophosphatemia, hypokalemia, hypocalcemia
- CKRT system clotting, clogging, downtime, and discontinuation of fluid removal due to patient instability.
- Inability to close surgical wounds due to edema

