## 13.2 SERIOUS ADVERSE EVENTS

Serious adverse event (SAE) collection begins after the patient or surrogate has signed informed consent and has received the study intervention or undergone study procedures. If a patient experiences a SAE after consent, but prior to receiving the study intervention, the event will NOT be collected unless the Principal Investigator feels the event may have

been caused by a protocol procedure. SAEs will be collected after initiation of study intervention until ICU discharge or day 28, whichever occurs first, regardless of the investigator's opinion of causation. Thereafter, SAEs are not required to be reported unless the investigator feels the events were unanticipated and related to the study procedure. If a determination is made that a SAE has a reasonable possibility of having been caused by a study procedure, it will be classified as a suspected adverse reaction. If the suspected adverse reaction is unanticipated, it will be classified as a serious unanticipated suspected adverse reaction (SUSAR).

As per the FDA and NIH definitions, a SAE is any adverse event that results in one of the following outcomes:

- Death
- A life-threatening experience (that is, immediate risk of dying)
- Prolonged inpatient hospitalization or rehospitalization

As per <https://www.fda.gov/safety/reporting-serious-problems-fda/what-serious-adverse-event> report if admission to the hospital or prolongation of hospitalization was a result of the adverse event. Emergency room visits that do not result in admission to the hospital should be evaluated for one of the other serious outcomes (e.g., life-threatening; required intervention to prevent permanent impairment or damage; other serious medically important event).

- Persistent or significant disability/incapacity

As per <https://www.fda.gov/safety/reporting-serious-problems-fda/what-serious-adverse-event> report if the adverse event resulted in a substantial disruption of a person's ability to conduct normal life functions, *i.e.*, the adverse event resulted in a significant, persistent or permanent change, impairment, damage or disruption in the patient's body function/structure, physical activities and/or quality of life.

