#### 13.3.1 IRB REPORTING

An AE or SAE is judged to be reportable to University of Pittsburgh HRPO, if it meets ALL of the following: i.) unanticipated in terms of nature, severity, or frequency; ii.) related or possibly related to study intervention; iii.) places subjects or others at a greater risk of physical, psychological, economic or social harm than was previously known or recognized. If the AE is judged to be reportable to the IRB based on above criteria, then the study team at the University of Pittsburgh will report to the HRPO within 10 working days. If it is an SAE and meets the above criteria, the study team will report to the HRPO within 24 hours.

All SAEs that meet above criteria and occurring at Mayo Clinic must be reported to the study team at University of Pittsburgh within 24 hours. All AEs that meet above criteria and occurring at Mayo Clinic must be reported within 5 working days to the team at University of Pittsburgh. The study team at University of Pittsburgh will then report all AE and SAE to the University of Pittsburgh HRPO within timelines shown in Table 7. The AEs that comprise the safety outcomes will be included in outcome reporting and will not be reported a second time as AEs or SAE.

At both clinical sites the study personnel must alert the Principal Investigator of any serious and study procedure-related adverse event within 24 hours of investigator/coordinator awareness of the event. Please note that most AEs will not meet the definition of an Unanticipated Problem Involving Risk to Subjects or Others and need not be reported to the HRPO. Expected AEs or AEs which are determined by the investigator to be unrelated to the research intervention need not be reported to the IRB. The flow chart below provides an algorithm for determining whether an AE meets the definition of an unanticipated problem involving risk to subjects or others and whether it needs to be reported to HRPO.

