## F. TIME-EVENTS SCHEDULE

### F1. GENERAL DATA COLLECTION

Measurement/Event	Screening	Baseline/ Day 0@	1	2	3	4	5	6	7	8- 14	15- 21	22- 28
Serum Creatinine	X	X	X	X	X	X	X	X	X	X	X	X
Demographics, History and Physical		X										
AKI Cerner alerts	X	X										
Etiology of AKI		X										
APACHE II		X										
Weight*		X	X	X	X	X	X	X	X	X	X	X
Daily FB*		X	X	X	X	X	X	X	X	X	X	X
Restrictive UF NET		X	X	X	X	X	X	X	X	X	X	X
Liberal UF NET		X	X	X	X	X	X	X	X	X	X	X
Ventilator parameters ΦΨ*		X	X	X	X	X	X	X	X	X	X	X
CKRT parameters ΦΨ\$		X	X	X	X	X	X	X	X	X	X	X
ABG*		A	A	A	A	A	A	A	A	A	A	A
Fluids (intake/output)*		X	X	X	X	X	X	X	X	X	X	X
MAP*		X	X	X	X	X	X	X	X	X	X	X
CVP, CI, PPV, SVV, and other hemodynamic data*		A	A	A	A	A	A	A	A	A	A	A
Hypotensive & Hypertensive episodes \$%		X	X	X	X	X	X	X	X	X	X	X
Cardiac arrhythmias \$%		X	X	X	X	X	X	X	X	X	X	X
Use of rescue UF NET rates \$		X	X	X	X	X	X	X	X	X	X	X
Severe hypophosphatemia\$		X	X	X	X	X	X	X	X	X	X	X
Severe hypokalemia\$		X	X	X	X	X	X	X	X	X	X	X
Severe hypocalcemia		X	X	X	X	X	X	X	X	X	X	X
All lab data*		X	X	X	X	X	X	X	X	X	X	X
Vital signs and medications*		X	X	X	X	X	X	X	X	X	X	X
Inability to close surgical wounds		X	X	X	X	X	X	X	X	X	X	X
New organ dysfunction*		X	X	X	X	X	X	X	X	X	X	X
Secondary infections		X	X	X	X	X	X	X	X	X	X	X
SOFA score β*	X	X	X	X	X	X	X	X	X	X	X	X
Vital status		X	X	X	X	X	X	X	X	X	X	X

Measurement/Event	Screening	Baseline/ Day 0@	1	2	3	4	5	6	7	8- 14	15- 21	22- 28
KRT Status		X	X	X	X	X	X	X	X	X	X	X
IHD use			X	X	X	X	X	X	X	X	X	X

X= Required

A=When available

Ψ=Data gathered at times indicated or until 72 hours, whichever occurs first

β=Records clinically available creatinine, platelets, bilirubin, MAP, SBP, FiO2, fluid bolus and vasopressor use

ϕ=Measure during reference period (0600 -1000); other values may be obtained closest to 0800 on the specified calendar date

\* = collected only if the patient is still in the ICU before day 28 and if available in the electronic health records

\$\_= collected only if the patient is on CKRT upto 24 hours following discontinuation of CKRT

%=collected only if the patient is on IHD

@ =Data collected before initiation of study intervention

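### SAP 5.2.2 counts safety outcomes only to 12 hours after CKRT stops, a cut-off the protocol never uses, so collected events may be left out of the safety comparison

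*SAP*

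**What the plan says.** The SAP sets one window for the safety outcomes it goes on to define in 5.2.2.1 to 5.2.2.8, which are adjudicated "from intervention initiation to 12 hours following discontinuation of CRKT". Those subsections cover the intradialytic events (hypotension, hypertension, arrhythmia, electrolytes), rescue UFNET, open surgical wounds, secondary infections, and new organ dysfunction. The last of these includes wound infection, pressure ulceration and thrombosis. No reason is given for 12 hours.

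The protocol uses other windows:

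- Attribution (13.1): "AEs will be considered related or possibly related to study treatment only up to 24 hours following discontinuation of CKRT".
- Collection of certain events (footnote to Appendix F1): "collected only if the patient is on CKRT upto 24 hours following discontinuation of CKRT".
- Monitoring (13.1): the investigators "will monitor for all AEs from study enrollment until ICU discharge or day 28, whichever occurs first".
- Serious events (13.2): "SAEs will be collected after initiation of study intervention until ICU discharge or day 28, whichever occurs first".
- Data for compliance, safety and between-group differences (8.3.2): recorded "until death, discharge from the ICU, or day 28, whichever occurs first".

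Protocol 13.3.1 adds: "The AEs that comprise the safety outcomes will be included in outcome reporting and will not be reported a second time as AEs or SAE".

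For analysis, the footnote to SAP shell Table 3 says that the safety P values compare percentages of patients with an event. SAP Appendix A analyses episodes of hypotension, hypertension, arrhythmia and filter clotting by GLMM. No exposure time or offset is specified.

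**The concern.** An analyst cannot apply a 12-hour cut-off and also report everything that the protocol collects for safety. Two things are at stake.

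First, completeness. One cut-off tied to the end of CKRT is applied to outcomes that can occur after CKRT has ended. Events that the sites record under the protocol would then be missing from the table that compares the arms.

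Second, comparability. The window closes when CKRT stops. Duration of kidney replacement therapy is a secondary outcome, and the protocol says that strategy may affect it. If duration differs by arm, patients are observed for different lengths of time, and a percentage of patients with an event mixes the event rate with the time at risk.

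**Working it through.** The plan states no figure to reproduce on this point. The main check is a comparison of the texts, followed by an illustration of how the window depends on CKRT duration.

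**1. Windows side by side**

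| Outcome | Protocol | SAP 5.2.2 |
|---|---|---|
| Hypotension, hypertension, arrhythmia, rescue UFNET, hypophosphatemia, hypokalemia | Collected to 24 h after CKRT (Appendix F1) | 12 h after CKRT |
| Inability to close surgical wounds | Through day 28, no CKRT limit (Appendix F1) | 12 h after CKRT |
| New organ dysfunction (with wound infection, pressure ulceration, thrombosis in 13.1) | While in the ICU, to day 28 (Appendix F1) | 12 h after CKRT |
| Secondary infections | Through day 28, no CKRT limit (Appendix F1) | 12 h in 5.2.2; no end time in 5.2.2.8 |
| All adverse events | ICU discharge or day 28 (13.1) | Not addressed |

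The SAP is also uneven within itself. SOFA-based organ failure as a secondary outcome (5.2.1.4) is followed to death, hospital discharge or day 28. SOFA-based new organ dysfunction as a safety outcome (5.2.2.7) falls under the 12-hour rule.

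**2. Window length**

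Window W = D + t, where D is CKRT duration and t is the tail (0.5 or 1.0 day). Protocol 5.2.8 reports an average D of 4 days. That is total CKRT duration in a pre-trial feasibility estimate based on one hospital, so it is only a stand-in. The SAP window starts at intervention initiation, and patients may have had up to 48 hours of fluid removal before enrollment.

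- 12 h tail: 4 + 0.5 = 4.5 days.
- 24 h tail: 4 + 1.0 = 5.0 days.
- Window time lost: 0.5 / 5.0 = 10%.

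**3. Sensitivity to a between-arm difference in CKRT duration**

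The difference d is an assumption; the documents give none.

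| d (days) | Ratio of windows, 12 h tail | Ratio of windows, 24 h tail |
|---|---|---|
| 0 | 1.00 | 1.00 |
| 1 | 5.5/4.5 = 1.22 | 6.0/5.0 = 1.20 |
| 2 | 6.5/4.5 = 1.44 | 7.0/5.0 = 1.40 |
| 3 | 7.5/4.5 = 1.67 | 8.0/5.0 = 1.60 |

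**4. Effect on the percentage of patients with an event**

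Assume a constant hazard λ, equal in both arms, so P = 1 − exp(−λW) and λ = −ln(1 − p)/4.5, where p is the percentage in the arm with the shorter CKRT. Take p = 43.2% (intradialytic hypotension in a trial cohort, protocol 5.2.5) and, as an assumption, p = 20%. The chance of p<0.05 is for a two-sided comparison of two proportions with 56 per arm (protocol sample size), ignoring clustering and covariates. The tail is 12 h.

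| d (days) | From 43.2% to | Chance of p<0.05 | From 20% to | Chance of p<0.05 |
|---|---|---|---|---|
| 1 | 49.9% | about 10% | 23.9% | about 7% |
| 2 | 55.8% | about 26% | 27.6% | about 15% |
| 3 | 61.0% | about 47% | 31.1% | about 27% |

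Example for d = 2: λ = 0.5656/4.5 = 0.1257 per day, and 1 − exp(−0.1257 × 6.5) = 55.8%. With a 24 h tail, the same λ and d = 2 give 46.7% against 58.5%. The gap is 11.9 points instead of 12.6 (from unrounded values). The longer tail removes the conflict between the documents but hardly any of the dependence on duration.

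**The case against.** The 12-to-24-hour interval is small for the events that the 24-hour footnote covers. Rescue UFNET needs CKRT to be running, and the SAP labels the hemodynamic, rhythm and electrolyte events intradialytic, so few could be counted after CKRT unless it restarts. The 24-hour sentence in protocol 13.1 is a rule on relatedness, not a counting window for every outcome. Both points stand. They move the weight of the concern to the non-dialytic outcomes.

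A reader might infer that follow-up does differ by arm. The documents do not support that. Protocol 5.3.2 says that the restrictive strategy may prolong kidney replacement therapy. Sections 5.2.1 and 11.2 point the other way, linking higher or liberal rates to longer dependence. No size is given.

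A reader might also infer that the SAP counts only 4.5 of 28 days. That does not follow: the four-day figure is not the trial's window, and protocol monitoring ends at ICU discharge if that comes first. Nor do the documents say when infections, ulcers or thromboses usually appear, so no claim about their timing is made here.

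Finally, a reader might conclude that late harms are discarded. They are not lost to oversight. Serious events are collected to ICU discharge or day 28 whatever the cause, and the DSMB reviews all adverse events (protocol 13.3.2). What may be lost is their place in the comparative table. Protocol 13.3.1 limits the backup, because safety-outcome events are not reported again as adverse events.

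The trial is not powered for adverse events (protocol 11.3), and the safety P values are not adjusted for multiplicity. That lowers the stakes but does not settle which window applies.

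**Conclusion.** The conflict is real and lies in the current text of both documents. The SAP's 12-hour window matches nothing in the protocol and, if followed, may leave collected events out of the safety comparison. The outcomes most exposed are open surgical wounds, new organ dysfunction, wound infection, pressure ulceration and thrombosis. Secondary infections are ambiguous because SAP 5.2.2.8 gives no end time. The number of events lost cannot be derived from the documents.

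Distortion from unequal windows is conditional. It is zero if CKRT duration is the same in both arms. The percentages in the illustration rest on a four-day duration, a constant and equal hazard, and an assumed difference of one to three days. They show the mechanism and do not predict a result.

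No primary outcome is affected. The safety results are meant to inform a phase III trial, so the window should be settled before analysis.

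**What to change.** Amend SAP 5.2.2 to state the window for each outcome:

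- Intradialytic events: from intervention start to 24 hours after CKRT stops, as in the protocol.
- Non-dialytic outcomes: from intervention start to ICU discharge or day 28, whichever comes first, which is the protocol's monitoring period. Give secondary infections this end time explicitly.

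Both windows end at an event that follows randomization; ICU length of stay is itself a secondary outcome. So also report observation time by arm, and put event rates beside the percentages: per CKRT-day for intradialytic events and per day at risk for the others.

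The cost is SAP wording and slightly more analysis. The protocol already plans collection over these periods, and the SAP needs revision anyway: it describes 144 patients in 6 ICUs, while the protocol describes 112 in 10. The downside is that later events are less specific to the intervention, which the table should say.

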#### 5.2.2.1 *Intradialytic hypotension*

Intradialytic hypotension will be defined as a new MAP  $<65$  mmHg, SBP  $<90$  mmHg or a decline in SBP  $>40$  mmHg, and/or a  $>30\%$  increase in dose of existing vasopressors, initiating a new vasopressor, administration of fluid bolus, or discontinuation of fluid removal with a goal to maintain (MAP)  $\geq 65$  mmHg, systolic blood pressure (SBP)  $\geq 90$  mmHg.

#### 5.2.2.2 *Intradialytic hypertension*

Intradialytic hypertension will be defined as new onset SBP  $\geq 160$  mmHg or MAP  $\geq 80$  mmHg for more than 1 hour in the absence of any vasopressor or inotrope use.

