#### 5.8.3 SAFETY OUTCOMES

1. Intradialytic hypotensive episodes
2. Intradialytic hypertensive episodes
3. Intradialytic new onset cardiac arrhythmias including supraventricular tachycardia, bradycardia, atrial fibrillation, ventricular tachycardia, ventricular fibrillation, and cardiac arrest
4. Emergent use of rescue UFNET with rates higher than the assigned treatment arm
5. Severe hypophosphatemia (<0.5 mg/dL)
6. Severe hypokalemia (<3.0 mg/dL)
7. Severe hypocalcemia (<1.90 mg/dL or ionized calcium <0.90 mmol/L)
8. CKRT system downtime due to hemofilter clotting or clogging
9. Discontinuation of UFNET due to hemodynamic instability
10. Inability to close surgical wounds due to edema
11. New organ dysfunction
12. Worsening of systolic or diastolic cardiac function on echocardiogram
13. Worsening of pulmonary edema on chest X Ray and or/or CT scan
14. Worsening of ileus on abdominal X Ray and/or CT scan
15. Bowel ischemia or anastomotic breakdown based on intraoperative findings
16. Pressure ulcerations
17. New wound infections
18. New arterial or venous thrombosis
19. Severe anemia requiring red cell transfusions
20. Severe thrombocytopenia requiring platelet transfusions
21. New secondary infections

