## 10 DATA COLLECTION AND SITE MONITORING

### 10.1 DATA COLLECTION

At the UPMC and the Mayo Clinic, the research staff will collect data and record it either on paper data sheets and/or enter in a secure web database. Once daily, coordinators will enter data that can be analyzed for consistency.

In this trial, we will define protocol deviation as delivered  $UF_{NET}$  rate that lies  $>0.5$  mL/kg/h outside of the target  $UF_{NET}$  rate range in the assigned treatment group for greater than six consecutive hours during fluid removal *without* significant changes in MAP (*i.e.*, MAP  $<65$  mmHg or  $\geq 90$  mmHg). As such, out of range,  $UF_{NET}$  rates  $>0.5$  mL/kg/h beyond the target  $UF_{NET}$  rate range in the assigned treatment group will not constitute a protocol deviation when the bedside team titrated the  $UF_{NET}$  rate as required to manage the patient hemodynamics (*i.e.*, when clinicians appropriately decreased rate or stopped  $UF_{NET}$  for MAP  $<65$  mm Hg or increased rate for MAP  $\geq 90$  mm Hg).

We will also calculate “%on target” value for each center for each of the monitored variables (# of dates on-target for a specific variable/# of opportunities to be on-target for that specific variable). Principle Investigators at each site will receive monthly reports of (1) % on-target for each of the specific variables in the most recent month; (2) % on-target for each of the variables since the beginning of a trial; and (3) a list of dates/times from the past month, the specific data that were entered for those dates/times, and determinations of on- or off-target.

Investigators will use these reports to identify aspects of protocol management that can be improved at their sites. The on-target performances of all ICUs will also be included, allowing investigators at each center to know how their ICU is performing related to other ICUs. On-target performances will be discussed during regular meetings of the Steering Committee.

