### 4.2.2 PROTOCOL ADHERENCE

We have defined protocol deviation *a priori* as delivered UFNET rate that lies  $>0.5$  mL/kg/h outside of the target UFNET rate range in the assigned treatment group for greater than six consecutive hours during fluid removal *without* significant changes in MAP (*i.e.*, MAP  $< 65$  mmHg or  $\geq 90$  mmHg). As such, out of range UFNET rates  $>0.5$  mL/kg/h beyond the target UFNET rate range in the assigned treatment group will not constitute a protocol deviation when the bedside team titrated the UFNET rate as required to manage the patient hemodynamics (*i.e.*, when clinicians appropriately decreased rate or stopped fluid removal for hypotension; increased fluid removal rate for hypertension or for treatment of respiratory distress due to fluid overload and pulmonary edema).

We will report the following stratified by restrictive and liberal UFNET rate groups: i.) no. of occurrences of deviations for six consecutive hours divided by UFNET days (mean events per day); ii.) no. of days with UFNET out of range for at least six consecutive hours; iii.) no. of patients with at least one occurrence of UFNET rate out of range for six consecutive hours. The proportion of patients with protocol deviation will be compared using the Wald test for GLMM and adjusted for prespecified covariates.

As an exploratory analysis, we will also report the proportion of total hours of UFNET rate within, above, or below range for each patient weighted equally and proportionally to total hours of fluid removal.

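### A MAP of 80 to 89 mmHg is a hypertensive safety event in SAP 5.2.2.2 but no significant change under the protocol-deviation rule, and the two limbs of the safety definition do not correspond

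*SAP*

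**What the plan says.** The only numeric definition of this safety outcome is in SAP 5.2.2.2. It opens "Intradialytic hypertension will be defined as new onset SBP" ≥160, adds MAP ≥80 as an alternative, and closes "mmHg for more than 1 hour in the absence of any vasopressor or inotrope use". The protocol lists "Intradialytic hypertensive episodes" among its safety outcomes (5.8.3) and gives no threshold.

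The protocol-deviation rule also uses MAP. SAP 4.2.2 and Protocol 5.8.1 and 10.1 count an out-of-range rate lasting more than six hours as a deviation only where there are no "significant changes in MAP", which they specify as MAP <65 or ≥90. Certain rate changes are then excused. SAP 4.2.2 excuses the case where clinicians "increased fluid removal rate for hypertension or for treatment of respiratory distress", with no number in that clause, and Protocol 5.8.1 does much the same. Protocol 10.1 puts numbers on it: the exemption applies "when clinicians appropriately decreased rate or stopped" fluid removal for MAP <65, "or increased rate for MAP" ≥90.

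**The concern.** The plan uses two MAP boundaries for raised pressure, 10 mmHg apart, and does not explain the difference. A patient in the gap is recorded as having a treatment-related type of harm by one rule and as haemodynamically unchanged by the other.

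Two things are at stake. The first is the meaning of the safety count. SAP shell Table 3 tests the percentage of patients with the event, and the DSMB reviews adverse events by group (Protocol 13.3.2). If the event admits unremarkable pressures, a difference or a lack of difference between arms is hard to interpret. The second is the exemption for rate increases. SAP 4.2.2 names hypertension without a cut-off in the exempting clause, and the only section of the SAP that defines hypertension uses MAP ≥80. An upward deviation while MAP is 80 to 89 could then be excused by one reader and counted by another, and the number of participants with a protocol deviation is a primary outcome.

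**Working it through.** The documents state no event rate or power for this outcome, so there is no figure to reproduce. The main check sets the thresholds side by side.

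| MAP, no vasopressor or inotrope | SAP 5.2.2.2 (MAP limb, if new and >1 hour) | Deviation rule (SAP 4.2.2, Protocol 5.8.1, 10.1) |
|---|---|---|
| 65 to 79 | not an event | no significant change |
| 80 to 89 | hypertensive event | no significant change |
| 90 and above | hypertensive event | significant change |

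The conflict is confined to the band from 80 to just under 90. As a further internal marker, the SOFA table in the SAP gives a cardiovascular score of 0 to any MAP ≥70 without vasopressors, so the whole of this band scores 0.

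**Do the two limbs correspond?** Assume the usual approximation MAP = (SBP + 2 × DBP)/3.
- 110/65: (110 + 130)/3 = 80.
- 120/60: (120 + 120)/3 = 80.
- Diastolic needed for MAP 80 at SBP 160: (3 × 80 − 160)/2 = 40.

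So SBP ≥160 with DBP ≥40 always meets the MAP limb, and the SBP limb adds only readings with a diastolic below 40. In the other direction, the MAP limb is met at systolic pressures 40 to 50 mmHg below 160. (A pressure of 120/80 gives MAP 93 and exceeds both cut-offs, so it does not illustrate the conflict.)

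**How many patients might be counted?** The documents give no MAP distribution. For illustration, assume normally distributed MAP in unsupported patients with mean 70 to 85 and SD 8 to 12. The share at or above a cut-off c at a single reading is 1 − Φ((c − mean)/SD).
- c = 80: from 11% (mean 70, SD 8; z = 1.25) to 73% (mean 85, SD 8; z = −0.625).
- c = 90: from 1% (mean 70, SD 8; z = 2.5) to 34% (mean 85, SD 12; z = 0.417).

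These shares precede the new-onset and one-hour conditions, which would lower them by an unknown amount.

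**Does the lower cut-off stop the outcome separating the arms?** Take 56 per group (Protocol 9.1), two-sided alpha 0.05, and ignore clustering and period effects. Power = Φ{[|p₂ − p₁| − 1.96 √(2p̄(1 − p̄)/n)] / √([p₁(1 − p₁) + p₂(1 − p₂)]/n)}. Assume SD 10 and a 5 mmHg difference in mean MAP between arms.

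| Lower-arm mean MAP | Power, MAP ≥80 | Power, MAP ≥90 |
|---|---|---|
| 70 | 0.47 | 0.20 |
| 75 | 0.54 | 0.33 |
| 80 | 0.54 | 0.47 |
| 85 | 0.47 | 0.54 |
| 90 | 0.33 | 0.54 |

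Neither cut-off is uniformly weaker.

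A second scenario looks at dilution. Assume true event rates of 10% and 30%, and that a fraction q of patients is flagged whatever the arm, so that each rate becomes q + (1 − q)p. Power is 0.76 at q = 0, 0.32 at 0.3, 0.19 at 0.5, 0.08 at 0.8 and 0.06 at 0.9. At q = 0.5, for example, the rates are 55% and 65%. Non-specific counting can therefore cost a good deal, but discrimination disappears altogether only as q approaches 1.

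**The case against.** The best defence is that the two rules do different jobs. One excuses out-of-range rates lasting more than six hours; the other counts events lasting more than one. Nothing in the documents says they must share a cut-off. The safety definition also carries three restrictions: new onset, more than an hour, and no vasopressor or inotrope. Protocol 13.1 adds a filter, since the case report forms take new hypertensive episodes that the investigator judges related to the rate of fluid removal or of uncertain relationship. This is one of 21 safety outcomes in a trial that Protocol 11.3 says is not powered for adverse events. A nearly redundant SBP limb does no harm in an either-or definition.

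Much of that stands, and it rules out several stronger readings that a reader might infer:
- That stable patients will be flagged, or nearly all of them. The restrictions above and the absence of MAP data allow only that they can be. A patient steadily at MAP 80 before the intervention is not plainly a new-onset event.
- That the outcome cannot discriminate between arms. The calculations do not show this. SAP 3.5.3 also lists a number of episodes, which could differ even if most patients had one.
- That the low cut-off creates a spurious excess in the arm with less vasopressor use. Any such effect comes from the no-vasopressor clause, would arise at any MAP cut-off, and would survive the change proposed here.
- That the SAP definition governs the deviation exemption. SAP 4.2.2 gives MAP ≥90 in the sentence before the exemption, and Protocol 10.1 says so outright. The wording is open, but ≥90 is the more natural reading there.

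The defence does not account for the gap itself. Different purposes might justify different cut-offs, but neither document offers that reason, and both rules use hypertension as the name for the state concerned. The redundancy of the SBP limb matters less than what it reveals: the two limbs describe quite different degrees of raised pressure.

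**Conclusion.** The inconsistency is real and can be read directly from the text. MAP from 80 to just under 90 is a hypertensive safety event in SAP 5.2.2.2 and no significant change in SAP 4.2.2 and Protocol 5.8.1 and 10.1. The SBP and MAP limbs do not correspond; that part rests on the standard MAP approximation. Followed as written, the only numeric definition can record as harm a pressure that the plan elsewhere treats as unremarkable, so the outcome may be non-specific.

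The size of the effect on event counts cannot be fixed from the documents. The illustrative ranges of 11 to 73% against 1 to 34% depend wholly on assumed means and SDs and apply to a single reading. This should be corrected, but it does not undermine the primary comparison of delivered rates.

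**What to change.** Reconcile the MAP cut-off in SAP 5.2.2.2 with the one in the deviation rule, and make the SBP and MAP limbs correspond. Then tie the hypertension exemption in SAP 4.2.2 and Protocol 5.8.1 to that single stated definition, consistently with Protocol 10.1. Which value is right is a clinical decision for the sponsor, and none is proposed here.

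The cost is mainly SAP wording, with a matching clarification in Protocol 5.8.1. MAP and vital signs are already in the Protocol Appendix F schedule, so no new data are needed. If the sponsor's choice raises the MAP limb, fewer events will be counted.
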